3.3. Exclusion Criteria

1. Subject must not be currently undergoing any medical or surgical procedures resulting in unstable vision.
2. Subjects for whom their vision, for whatever reason, can be considered unstable.
3. Subjects who have undergone cataract, refractive, or other surgical procedures related to vision in the six month period prior to the study.
4. Subjects who have undergone any eyesight-related injections (e.g. anti-VEGF) in the six month period prior to the study.
5. Subjects unable or unwilling to adhere to the examination schedules as they are described in the study protocol. This may also include Subjects already enrolled who, for whatever reason become unable or unwilling to continue the study. This may also include subjects for whom the travel time to/from the study site is unacceptable.
6. Subjects who self report a history of alcoholism or use of illegal drugs, Subjects who exhibit clinical evidence of depression, poor motivation, emotional or intellectual problems, who are deemed unsuitable psychologically or physiologically for study participation by the investigator.
7. Subjects who may have a conflict of interest with eSight Corp, which could reasonably influence their participation in the study.

4. Study Design

The Quality of Life and Functional Visual Improvement Study Using eSight Wearable Video Eyewear is a prospective multi-site study. The main elements of the study are shown in the flowchart below. Decision points are shown as diamonds. Note that the flowchart below only shows activity for the extended arm (n=60), not the larger screening arm.

As indicated on the chart, the red boxes are activities conducted by eSight. The green and blue boxes are conducted at the study site, by a research assistant, Occupational Therapist, Certified Low Vision Therapist or Eyecare Physician respectively (or supervised and trained designate). Over the course of the study there are four visits by the subject to the study site as indicated by the larger grey boxes. Tests conducted during the first visit are without the eSight device. Subsequent tests deploy the eSight device. Tests within each visit (grey boxes), do not necessarily need to be in the order presented above.

Note that the Case Report Form (CRF) that will be used for the eQUEST Study will be Microsoft Excel spreadsheet with appropriate constraints (restricted cells, validated data entry, drop down choices, help text, etc.). Each site will be provided with a tablet computer with the CRF pre-installed. This will help to ensure data completeness and integrity. Each section of the CRF will identify the level of staff (eSight or Study Site) that is required to conduct that portion of the protocol. Information provided to the Study sponsor will be de-identified.

The components of the study are described in greater detail in Section 4.1 below:

4.1. Schedule of Events

This section indicates data that will be collected for each subject. Subjects will be screened for enrollment prior to their initial visit. At the initial visit, subjects will provide informed consent and the investigator will obtain medical and ophthalmic history information as described in the CRF, and conduct a complete low vision assessment.

At various points through the protocol, decision points are identified as red boxes below.

STEP 1: Pre-Screen, Subject Profile, and Informed Consent

The Eyecare Physician at the Study Site will select potential candidates from the Site's regular flow of patients. In some cases, eSight may direct interested persons to the Site, who have contacted eSight directly.

Steps 1.01 through 1.03 may be administered by a Research Assistant or a similarly suitable staff person at the clinic (e.g.: CLVT, OT, etc.).

Step 1.01 Subject ID: When a potential Study Subject has been identified, the Site Administrator will assign a unique subject identification number from the site-specific list of numbers provided by eSight.

Step 1.02 Demographic Data: The Site Administrator will contact prospective study participants and obtain demographic data.

Step 1.03 Inclusion/Exclusion, and Informed Consent: The Site Administrator will work through the inclusion/exclusion criteria to verify the subject is qualified for the study, and then work with the subject through the informed consent process, obtaining their written approval to proceed. An IRB approved informed consent form will be used.

The site administrator will then provide to the Third Party Surveyor, contact information for the study subject in order to proceed with Step 2 below. The Third Party Surveyor will complete Step 2 and send that information back to the Site Manager for inclusion in the Subject's CRF.

STEP 2: Pre-Study LV Inventory Assessment & VA LV VFQ-48

Steps 2.01 through 2.03 will be administered by telephone using a Third Party Surveyor¹⁷.

Step 2.01 AT Inventory: The Third Party Surveyor will conduct a telephone interview with each subject. The purpose of this phone interview is to inventory the subject's current assistive devices and usage habits. This background information will be used by the study examiner to determine which visual aids will be used during benchmarking activities.

Step 2.02 Baseline VA LV VFQ-48 Questionnaire: Third Party Surveyor will work with the subject to complete the VA LV VFQ-48¹⁸ questionnaire.

Step 2.03 Baseline eSight-8 Questionnaire: Third Party Surveyor will work with the subject to complete seven QoL type questions which will provide predictive insights regarding their affinity with the eSight device.

Step 2.04 Advancement Decision: Based on the Subject's responses to 2.02 and 2.03 above the Eyecare Physician will determine whether or not the Subject ought to proceed through the Protocol.

Note: While not an explicit inclusion criterion, there are seven questions on the VA LV VFQ-48 items identified in red (2, 3, 5, 12, 14, 19, 45) for which the eSight Eyewear device has been shown to be particularly effective. If a subject scores four or more of these items as "moderately difficult" or "extremely difficult", they will be considered a strong candidate.

STEP 3: Clinic Visit – LV Assessment & eSight Demonstration

Subjects will also be asked to complete a series of supervised activities to establish a baseline of their visual function and functional visual performance *without* eSight Eyewear¹⁹.

Duration: 2-3 hours.

Steps 3.01 through 3.04 may be administered by a Research Assistant or a similarly suitable staff person at the clinic (e.g.: CLVT, OT, etc.).

Step 3.01 Low Vision Rehabilitation Goals: The CRF form identifies five ADLs, prioritized by the subject, which they wish do (or do better). It also asks how satisfied they are currently with their ability to perform this task, and how important this task is to their day-to-day quality of life. The purpose of this step is provide the subject with specific goals that they can work to achieve (or improve) using eSight Eyewear over the course of the study.

¹⁷ In the case of Johns Hopkins University Wilmer Eye Institute, research assistants from the institute will conduct Step 2. These research assistants will be dis-associated from the PI and other researchers who have face-to-face interaction with the subject.

¹⁸ Using the VA LV VFQ-48 and LV VFQ-20 in Low Vision Rehabilitation, Stelmack, Massof, Optom Vis Sci. 2007 Aug;84(8):705-9.

¹⁹ Because we intend to deploy standardized ADL measures, it may be possible to compare our findings directly to some other interventions (e.g.: Haymes, Johnston, & Heyes, 2001).

Note: If, in the estimation of the researcher, the Subject identifies goals which are too abstract (e.g. “I want to do more”, “I want to be happier”), or not suitable uses for eSight Eyewear (e.g. “I want to swim”, “I want to drive”, “I want to go downhill skiing”), they will be encouraged to elaborate or identify a different goal that can be considered applicable to the Study/Device.

Step 3.02 Cognitive Assessment: To determine the cognitive capability of the subject to continue with the remainder of the study protocol, an assessment using the Montreal Cognitive Assessment – BLIND (MoCA)²⁰ test will be conducted. Psychometric properties of the MoCA in its full version include a test-retest correlation of $r = .92$, while internal consistency was evaluated with a Cronbach’s alpha of $.83$.²¹

While the cognitive suitability of the Subject for the test protocol is ultimately the decision of the researcher, a MoCA score of less than 20 indicates that careful consideration is necessary²². If the researcher determines that the subject is cognitively unsuited for the study, the remaining steps below are unnecessary (skip to 3.10).

Step 3.03 36-item short-form health survey (RAND SF-36)²³: The SF-36 is a brief questionnaire that provides a validated indication of the subject’s broad general health. It was chosen in part because of its excellent psychometric properties, which include a minimum of $.70$ for reliability statistics. Content, concurrent, construct, criterion, and predictive validity have been shown to be satisfactory (Ware & Gandek, 1998)²⁴

Steps 3.05 through 3.11 are administered by the Eyecare Physician or suitably trained and supervised clinical staff. These tests benchmark the subject’s visual performance with their habitual low vision aids where possible²⁵. As a minimum for these tests, the subject should wear their corrective lenses (distance or reading) as applicable. NOTE: if the lens prescription as

²⁰ “Sensitivity and Specificity of the Montreal Cognitive Assessment Modified for Individuals Who Are Visually Impaired”, Wittich, Phillips, Nasreddine, Chertkow, JVIB 06/2010; 104(6):360-368. See also: <http://www.mocatest.org>.

²¹ Nasreddine ZS, Phillips NA, Bedirian V, Charbonneau S, Whitehead V, Collin I, et al. The Montreal Cognitive Assessment, MoCA: a brief screening tool for mild cognitive impairment. J Am Geriatr Soc. 2005;53(4):695-9.]

²² The MoCA scoring tool does not provide regarding pass/fail criterion. Ultimately, a subject’s performance in the test is meant to provide clues to the researcher about cognitive deficiencies.

²³ Ware, Sherbourne. “The MOS 36-item short-form health survey (SF-36). I. Conceptual framework and item selection”. Med Care. 1992 Jun;30(6):473-83.

²⁴ Ware JE, Gandek B. Overview of the SF-36 Health Survey and the International Quality of Life Assessment (IQOLA) Project. J Clin Epidemiol. nov 1998;51(11):903-12.

²⁵ References: The forms provided with this study are a subset of LV rehabilitation practice guidelines from the following sources:

- a) Ontario Practice Template - Low Vision Assessment.
- b) New York Lighthouse for the Blind LV Intake Exam ([name]) <http://www.lighthouse.org/professionals/practice-management/structured-low-vision-exam>.
- c) VisionAware: <http://www.visionaware.org/info/your-eye-condition/eye-health/low-vision/low-vision-examination/1235>

determined in step 1.04 is substantially different from the subject's habitual glasses, this portion of the protocol may be conducted with a trial lens frame.

Step 3.04 Medical and Ophthalmic History: The clinician and/or site administrator will record the following information on the CRF:

- OD and OS disease type(s), and approximate number of years, if possible.²⁶
- Free-form field: other eye-health related history (e.g.: laser photocoagulation, Lucentis, etc.), considered by the examiner to be relevant.
- subject's verbal description of visual scotoma if present

Step 3.05 Refractive Prescription: The clinician will perform a refraction to determine the prescription lenses required by the subject for best distance and near vision. Note: No prism element may be included in the refraction prescription.

Step 3.06 Acuity Test: Choose ONE OF ETDRS or Snellen

ETDRS²⁷: Using the subject's habitual corrective lenses (if applicable). For each eye independently, and then binocularly, determine the ETDRS acuity.

- Determine the last row where the subject can correctly identify all 5 letters on that row.
- Determine the log score for that row (these scores are shown in the margin of the ETDRS test, e.g. the 20/25 line has a log score of 0.1)
- subtract 0.02 log units for every letter that is correctly identified beyond the last row where all of the letters are correctly identified.

For example: if the subject reads all of the letters correctly on the 20/32 row and then 3 letters correctly on the 20/25 row, the Log Score would be calculated as follows:

$$\begin{aligned} \text{ETDRS Acuity Log Score} &= 20/32 \text{ Row} = 0.20, \text{ plus } 3 \text{ letters on } 20/25 \text{ row} \\ &= 0.20 - (3 \times 0.02) \\ &= 0.14 \end{aligned}$$

Snellen: Using the Subject's habitual corrective lenses (if applicable). For each eye independently, and then binocularly, determine the Snellen acuity²⁸.

Step 3.07 Mars Contrast Sensitivity Test: Test Contrast Sensitivity using the Mars chart. Mars test score sheet to be provided²⁹.

²⁶ On the CRF this will be a date range, because subjects will not recall with accuracy. E.g.: <6mos, 6-12mos, 1-2yrs, 2-5yrs, 5-10yrs, >10yrs.

²⁷ <https://www.good-lite.com/Details.cfm?ProdID=639>

²⁸ In some cases (e.g. dense scotoma) the test Subject may have difficulty reading ALL 5 letters on any line of the ETDRS chart, which limits the precise ETDRS scoring algorithm above. Adding Snellen allows greater flexibility in participant inclusion and data analysis.

²⁹ © 2003-2004 The Mars Perceptrix Corporation. <https://www.good-lite.com/Details.cfm?ProdID=549&category=26&Secondary=71>

Step 3.08 eSight Demonstration: eSight Eyewear will be demonstrated using a clinician's version of the device³⁰. The subject will be provided basic instruction on its use (zoom in/out, contrast adjust). The researcher will observe the Subject's performance in tests of, acuity (ETDRS) contrast performance, facial recognition, and reading (MNRead). These above tests are observational only, and are not recorded to provide a baseline performance measure with the eSight Device.

Step 3.09 Advancement Decision: At this point in the protocol the Subject and the Eyecare Physician will come to an agreement about whether to continue with the extended portion of the protocol evaluating eSight Eyewear. The decision will be based on a minimum 4-line ETDRS improvement using the device, the subject's performance of the various tasks above, their impressions of the eSight Eyewear demonstration, and the continued compliance with inclusion/exclusion criteria as defined in Sections 3.2 and 3.3 respectively. There is a subjective and personal aspect to this decision, not unlike a patient's decision about whether or not to purchase the device.

Should the subject and/or the examiner decide not to proceed with the remainder of the study, this should be noted on the CRF, along with their reason for withdrawal.

Step 3.10 Microperimter Test (without eSight): This test is optional. Bilateral. The intent is to understand how field performance correlates with efficacy results. Because this diagnostic test requires a significant time commitment, the subject will be asked for consent, as indicated on the CRF. Ideal candidates for this test are <60 years old, with a central scotoma in both eyes. A 10-2 pattern is preferred. Indicate on the Case Report Form which test was conducted.

Steps 3.11 through 3.13 may be administered by a Research Assistant, or a similarly suitable staff person at the clinic (e.g.: CLVT, OT, etc.).

Step 3.11 Minnesota Low Vision Reading Test (MN READ): Under normal "office" lighting conditions, using the hand held MNREAD charts, record the subject's score. Score sheets to be provided³¹. This test will be conducted without eSight Eyewear, using the Subject's habitual spectacle correction if applicable.

Step 3.12 Cohn-Kanade Facial Recognition Test: The subject will complete a task of recognizing the sex and facial expressions on a randomized selection of faces from the University of Pittsburgh Cohn-Kanade Facial Images Database. These will be displayed on a

³⁰ The clinician's version of eSight Eyewear is more adjustable (e.g. trial lenses, pupil distance, etc.), but compromises on weight, comfort and aesthetics. Subjects who receive eSight Eyewear for the trial will be provided a consumer version of the product, appropriately sized, incorporating their prescription lenses and correct pupil spacing.

³¹ Scoresheets will follow Lighthouse Low Vision Products format.

computer screen simulating faces at a distance of five feet and ten feet³². This test will be conducted without eSight Eyewear, using the Subject's habitual spectacle correction if applicable.

Step 3.13 Melbourne Low-Vision ADL Index Test (MLVAI)³³: The MLVAI is a series of standardized ADLs appropriate for the low vision population. The test has been modified for eQUEST to remove certain dated or impractical items. The intention of this test is to establish a benchmark performance for the various activities identified. This test will be conducted without eSight Eyewear, using the Subject's habitual spectacle correction if applicable.

STEP 4: Clinic Visit – Fitting & Baseline Testing with eSight Eyewear

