This study seeks to generate further evidence-based conclusions about the efficacy of eSight Eyewear for various ADLs in the low vision population. Specifically, the study seeks to understand how eSight Eyewear can be used to improve employee productivity and satisfaction in vocational, educational, and home settings.

An initial assessment was performed by the CNIB where 33 individuals of various age, vision and eye pathologies showed improved visual function for both distance and near vision using traditional visual assessment tests (distance acuity and contrast performance) using various image processing algorithms including variable magnification, adjustable contrast, and colour remapping techniques. The CNIB test did not include assessment of the Activities of Daily Living (ADLs) or seek to measure improved functional vision. To date there are ~400 “early-adopter” individuals with low-vision that wear the glasses in their day-to-day lives. Most users self-report high satisfaction with the device however, the technology has not been subject to rigorous scientific study to determine which users would most benefit from using this technology and how the glasses improve their functional visual performance and quality of life. Considering the high cost of this technology (\$15,000) this Clinical Study will guide patients and physicians on the expected benefits and indications for the large population affected with untreatable vision disorders.

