3.2. Inclusion Criteria

1. Male or female subjects between the ages of 13-75. The goal for the extended arm is that 50% of subjects will be 65 years of age or younger, and 50% will be older than 65¹⁴.
2. Subject must have distance BCVA measured with ETDRS of between 20:60 and 20:400 in the better eye.
3. Subjects have been diagnosed with a condition that presents as one or all of the following: Central scotomata, geographic atrophy, or scattered scotomata. These are typically symptoms attributed to conditions such as: Diabetic Retinopathy, Stargardt's Disease, Age Related Macular Degeneration, Leber's Disease, Retinopathy of Prematurity, Cone Rod Dystrophy, or Ocular Albinism¹⁵.
4. Subject must have an estimated functional field of view of at least 20 degrees (bilateral or monocular).¹⁶
5. If the subject is employed, they must be prepared to use eSight Eyewear in their workplace environment, have informed their employer of their involvement in the study, and received permission from their employer to bring eSight Eyewear into the workplace. If the subject is self-employed, they must be prepared to use eSight Eyewear in their

¹³ "Sample size estimation and power analysis for clinical research studies", Suresh & Chandrashekar, J Hum Reprod Sci. 2012 Jan-Apr; 5(1): 7-13. "G*Power 3: a flexible statistical power analysis program for the social, behavioral, and biomedical sciences", Erdfelder, Faul, & Buchner, Behav Res Methods. 2007 May;39(2):175-91.

¹⁴ The intention of this stratification of the cohort is to understand age effects related to the eSight Eyewear device. This stratification does not impact the statistical analysis in Section 3.1

¹⁵ These have been demonstrated by current eSight users to be conditions for which eSight Eyewear can provide significant benefit. For other conditions, especially those which present as peripheral degeneration encroaching inwardly ultimately towards the central vision, eSight Eyewear's effectiveness has not yet been convincingly demonstrated (e.g.: early stage Retinitis Pigmentosa, early stage Glaucoma).

¹⁶ Acuity and field criteria, while firm requirements here, are inflection points in the real world population. Evidence indicates that eSight users outside of the 20/60 – 20/400 BCVA and 20° field can still have success with the eSight device, but results are less consistent.

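### Current or previous eSight owners and home users are not excluded, so self-reported baselines and first with-device readings may already reflect earlier use

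*Combined protocol and SAP*

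**What the plan says.** **Recruitment.** Under Step 1 of Section 4.1 the eyecare physician selects candidates from the site's usual patients. It then adds: "In some cases, eSight may direct interested persons to the Site, who have contacted eSight directly". No share or cap is set for this route.

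**Existing users.** Section 1 says "To date there are ~400" early adopters, described as "individuals with low-vision that wear the glasses in their day-to-day lives". It also mentions an earlier assessment in 33 people. Footnote 15 in Section 3.2 says of the eligible diagnoses: "These have been demonstrated by current eSight users to be conditions for which eSight Eyewear can provide significant benefit".

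**Eligibility.** Neither Section 3.2 nor Section 3.3 mentions earlier ownership, trial or demonstration of the device. The nearest criterion is exclusion 7: "Subjects who may have a conflict of interest with eSight Corp, which could reasonably influence their participation in the study".

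**Later checks.** The Step 2.01 telephone interview is meant to "inventory the subject's current assistive devices and usage habits", so that the examiner can choose aids for benchmarking. Step 2.04 is an advancement decision: "Based on the Subject's responses to 2.02 and 2.03 above the Eyecare Physician will determine" whether the subject goes on. Step 2.01 is not named there.

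**Analysis.** Section 10 compares acuity, contrast and reading speed without the device at the start and with it at the end. It also compares initial and final VFQ and SF-36 scores. It plans to look at differences between sites, but not at earlier exposure or referral route.

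**The concern.** A before-and-after study with no control group depends on the starting state being a true before. If someone who already uses eSight answers the baseline questionnaires, part of the device's effect may already be in the initial score, and the change from initial to final shrinks.

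The same person comes to the Step 3.08 demonstration with practice. That may help in reaching the four-line improvement that Step 3.09 considers. They also start Step 4 above a novice's level. Section 2 lists learning curve among its objectives, and Step 9 is meant to show change over time with the device, so an experienced user at Step 4 leaves less change to see.

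Separately, people who approached the manufacturer may hold favourable expectations, and the outcomes are unblinded self-reports. The study is meant to guide patients and physicians on "the expected benefits and indications for the large population affected with untreatable vision disorders", so readers need to know how many participants came by which route and with what experience.

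**Working it through.** **1. Can a prior user pass the criteria as written?** Take a current or former user with a listed diagnosis, better-eye acuity between 20:60 and 20:400 and a field of at least 20 degrees.

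- Section 3.2: the eight criteria cover age, acuity, diagnosis, field, workplace use, motivation and competence, consent, and safe use. All can be met. By footnote 15, the diagnosis list was itself drawn from current users' experience.
- Section 3.3: exclusions 3 and 4 set six-month intervals for surgery and injections, but no exclusion sets one for the device. Exclusion 7 does not define conflict of interest, and being a customer is not plainly one.
- Step 2.01: shows current ownership, after eligibility has been verified at Step 1.03. It does not ask about past trials or demonstrations.
- Step 2.04: rests on Steps 2.02 and 2.03.
- Step 3.09: rechecks the criteria, but there is no prior-use criterion to recheck.

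Result: eligible as written.

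**2. Which measurements are affected?**

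- Acuity, contrast, MNREAD, faces and MLVAI at baseline: not affected in the sense of becoming with-device readings. Section 4 says first-visit tests are without the device, the introduction to Step 3 repeats this, and Steps 3.11 to 3.13 each state it.
- VFQ-48 and eSight-8 (Steps 2.02, 2.03), SF-36 (Step 3.03) and goal satisfaction (Step 3.01): open to carry-over. Section 4.1 does not tell a user to answer as if without eSight.
- Step 3.08 demonstration and Step 4 readings: not first exposures for a prior user.

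**3. The plan's own figure.** Section 3.1 gives n = 60 for a one-sided alpha of 0.05, power 0.95 and effect size 0.40 to 0.45. The test is not named; I assume a paired t-test. The exact calculation gives n = 70 at 0.40, 60 at 0.43 and 55 at 0.45, so 60 is reproduced within the stated range. The text of Section 3.1 names no outcome and makes no allowance for prior exposure, so no corrected sample size follows.

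**4. Can the bias be sized or signed?** Let d be the mean self-reported change in new users. Suppose k of the 60 are prior users whose baseline already holds the full benefit (change 0), and m sponsor-directed subjects report a change inflated by e. Then

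observed mean = [(60 − k)d + m·e] / 60 = d − (k/60)d + (m/60)e.

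Each such prior user removes at most 1/60 = 1.7% of d, and less if carry-over is partial. The two terms cancel when m·e = k·d. The documents give none of k, m or e, so neither the size nor the sign can be stated.

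**The case against.** The case against has several sound parts.

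- **The main objective comparison survives.** A reader might infer that an owner's habitual aids would include eSight, because the notes before Step 3.05 refer to benchmarking with habitual low vision aids where possible. Sections 4 and 4.1 do not support that: first-visit tests are expressly without the device. This stands in full and narrows the point.
- **Owners have little reason to enrol.** The device is lent for three months and returned at Step 9.09, and Section 1 prices it at $15,000. People who contact the manufacturer are most naturally prospective buyers. This makes large numbers of current owners unlikely. It does not rule out former users, or people who have had a trial or demonstration.
- **Step 2.04 is a partial filter.** A strong candidate rates at least four of seven VFQ-48 items as moderately or extremely difficult, which a contented current user may not do. The plan says this is not an explicit inclusion criterion, and a former user without the device could easily meet it.
- **Current ownership would be recorded at Step 2.01.** True. What Section 4.1 does not list is past exposure and referral route. The case report form is not among the documents and may have such fields.
- **Selection is declared.** Footnote 12 says the population is not random, and Section 3.2 asks for highly motivated subjects. This stands, so self-referral adds to a selection already acknowledged.
- **Everyone has a demonstration at Step 3.08.** A past brief demonstration therefore matters much less than ownership or home use. I accept this; it is why the fix records the former and excludes only the latter.

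**Conclusion.** The gap is real but limited. A current or previous owner or home user is eligible as written, a route from the sponsor to the sites exists, and no later step reliably stops such a person. The measurements at risk are the self-reported baselines, the demonstration result and the Step 4 to Step 9 change. The without-device performance baselines are sound.

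Two stronger conclusions are tempting. One is that existing users are in fact being enrolled; the documents do not say so, and linking the roughly 400 wearers to the referral route is only a possibility. The other is that the reported benefit will be overstated (or understated); carry-over and expectation pull in opposite directions, and nothing in the plan fixes the balance. I therefore give no percentage for the overall bias. The 1.7% per subject is a ceiling for carry-over on one self-reported mean, and it rests on the assumption of full carry-over.

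The point is worth acting on because the remedy is almost free, and past exposure and referral route are hard to reconstruct reliably afterwards.

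**What to change.** - **Section 3.3:** add an exclusion for current or previous eSight ownership or home use.
- **Step 1.02:** record the referral route (clinic's own patients or directed by eSight) and any earlier demonstration or evaluation of the device.
- **Section 10:** pre-specify a sensitivity analysis of the VFQ-48, SF-36 and Step 4-to-Step 9 changes that leaves out subjects with earlier exposure and those directed by the sponsor.

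The cost is one line of eligibility text, two data fields and one extra analysis, with a small loss of eligible candidates. The sensitivity analysis will have fewer than 60 subjects if any are left out, so it should be read for consistency with the main result and not as a separate test.
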